1. OBJECTIVES

1.1 Study Design

This is an open-label, single-arm, phase II study of bavituximab in combination with standard of care radiation and temozolomide in adult patients with newly diagnosed GBM. All patients will be treated with bavituximab weekly until 3 months after completion of chemoradiation or until there is radiographic or clinical evidence of disease progression or unacceptable toxicity.

1.2 Primary Objectives

The primary objective will be to determine the proportion of patients alive at 12 months (OS12).

1.3 Secondary Objectives

Secondary Objectives will include progression free survival and toxicity of bavituximab in this patient population.

2. BACKGROUND

2.1 Study Disease(s)

An estimated 51,410 primary brain tumors were diagnosed in 2007, and 19% of these tumors were glioblastomas (GBM) (CBTRUS 2008). GBM is the most common malignant primary brain tumor and is a uniformly fatal disease with 5-year survival rates less than 4% despite aggressive treatment with surgery, radiation and chemotherapy. Consequently, new therapies for this patient population are desperately needed.

2.2 IND Agent(s)

Oncologie, Inc. (hereinafter referred to as Oncologie, is developing bavituximab as an immunotherapeutic that is being investigated in the treatment of cancer. Bavituximab is a genetically engineered immunoglobulin gamma 1 (IgG1) chimeric (human/mouse) monoclonal antibody containing the variable region sequences of the murine phosphatidylserine (PS)-targeting mouse antibody 3g4 and human IgG1 κ constant region sequences. Bavituximab binds β 2-glycoprotein-1 (β 2-GP1) to form the complex of β 2-GP1 with PS. PS is a highly immunosuppressive molecule typically expressed inside the membrane of normal cells, but "flips" and becomes exposed on the outside of cells that line tumor blood vessels, tumor cells, and exosomes, creating a specific target for anticancer treatments.

Bavituximab is a viable immunotherapeutic approach because its primary mechanism of action involves modulating the tumor microenvironment from a primarily immunosuppressive, angiogenesis-promoting state (with infiltrating myeloid-derived suppressor cells [MDSCs] and m2-macrophages) to an immune-activating state (with long term tumor-specific immunity facilitated by m1 macrophages, mature dendritic cells, and activated t lymphocytes). This process occurs via fc-mediated signaling and direct cell killing (antibody-dependent cellular cytotoxicity). In essence, expression of PS on the external surface of the cell acts as an immunosuppressive signal in normal cell death and immune phagocytic clearance. Tumor PS exposure in the microenvironment is immunosuppressive in malignant transformation and progression. Thus bavituximab has been shown to overcome immune suppression and stimulate antitumor immunity in nonclinical models (DeRose 2011; Yin 2013).

Nonclinical Experience

Data suggest that PS is primarily responsible for expansion of MDSCs and M2-like tumorassociated macrophages (TAMs) in tumors, and that bavituximab could reverse this process and reactivate antitumor immunity. Treatment of tumor-bearing mice with docetaxel in combination with 2aG4 (a PS-targeting antibody and the murine precursor to bavituximab), has been shown to potently suppress the growth and progression of prostate tumors and increase the presence of M1-like TAMs and mature dendritic cells in the tumor microenvironment (Yin 2013).

The tumor and tumor vasculature localization of PS-targeting antibodies is followed by tumor immunity enhancing effects, tumor vessel damage, tumor vascularity reduction, tumor necrosis, and tumor growth retardation in multiple models (Ran 2005). The synergistic antitumor activity of antibodies targeting PS in combination with cytotoxic chemotherapy has been demonstrated in animal models, including but not limited to the Pan02 pancreatic adenocarcinoma cell line with gemcitabine and the MDA MB 435 cell line with docetaxel (Beck 2006, Huang 2005).

In toxicology studies, no target organs of toxicity were identified in rats (up to 20 mg/kg) and monkeys (up to 10 mg/kg) receiving weekly doses for 8 weeks of bavituximab, and minimal histological findings in heart and lung were noted when administered to monkeys at 100 mg/kg. Detailed information about comprehensive nonclinical safety, immunology, and pharmacokinetics (PK) is provided in the current Investigator's Brochure for bavituximab.

Clinical Experience

Bavituximab has been evaluated by Oncologie in clinical studies in over 800 patients (as of July 2016), most of whom were treated with combination therapy. These clinical trials have included patients with a number of tumor types, including breast, lung, pancreatic and hepatocellular carcinoma, and in chronic HCV. A dose of 3 mg/kg bavituximab given intravenously (IV) was determined and selected for further clinical study based on Phase 1 single-agent and combination therapy studies.

In a Phase II, multicenter, breast cancer trial (PPHM 0702), bavituximab (3 mg/kg), given weekly until progression, was combined with paclitaxel (100 mg/m2) and carboplatin (area under the concentration-time curve = 2), given on Days 1, 8 and 15 of planned 4-week cycles for up to 6 cycles, to 46 patients with metastatic disease, unrestricted by hormone or HER2 status. Objective response per Response Evaluation Criteria in Solid Tumors (RECIST) occurred in 34 of 46 patients (73.9%) with a median duration of response (DOR) of 3.7 months (95%)

confidence interval [CI]: 3.1, 5.8) and median PFS of 6.9 months (95% CI: 5.6, 7.7) (Jain 2010). The most common Grade 4 treatment-emergent adverse event (TEAE) was neutropenia (12 patients, 26.1%), and the most common Grade 3 TEAEs were leukopenia (11 patients, 23.9%), neutropenia (9 patients, 19.6%), and anemia (5 patients, 10.9%).

In a Phase II, multicenter, lung cancer trial (PPHM 0704), bavituximab (3 mg/kg), given weekly until progression, was combined with docetaxel (35 mg/m2), given on Days 1, 8, and 15 of planned 4-week cycles for up to 6 cycles, to 46 patients with MBC (with any hormone or HER2 status). Objective response occurred in 28 of 46 patients (60.9%) with median DOR of 6.1 months (95% CI: 5.7, 7.5) and median PFS of 7.4 (95% CI: 6.1, 9.1) months (Tabagari 2010). Of the most common TEAEs reported, only fatigue, headache, back pain, and hypertension were Grade \geq 3. In another Phase II, multicenter trial in patients with advanced nonsquamous nonsmall-cell lung cancer patients were randomized 1:1:1 to docetaxel 75 mg/m 2 every 21 days for up to 6 cycles combined with weekly, blinded infusions of placebo, bavituximab 1 mg/kg, or bavituximab 3 mg/kg until disease progression or unacceptable toxicity (Gerber 2016). Efficacy end points in the bavituximab 3 mg/kg group (n = 41) and in the placebo/bavituximab 1 mg/kg group (n = 80), respectively, were as follows: ORR, 17.1% (95% confidence interval [CI], 5.6%-28.6%) and ORR, 11.3% (95% CI, 4.3%-18.2%); median progression-free survival 4.5 and 3.3 months (hazard ratio [HR], 0.74 [95% CI, 0.45-1.21]; P = .24); median overall survival 11.7 and 7.3 months (HR, 0.66 [95% CI, 0.40-1.10]; P = .11). Toxicities were manageable and similar between arms.

In a single-center, investigator sponsored study, breast cancer patients received bavituximab 3 mg/kg weekly in combination with paclitaxel (80 mg/m2) given on Days 1, 8, and 15 in 4-week cycles to 14 patients with HER2-negative MBC. Treatment resulted in an ORR of 85% (2 patients had complete responses) and a median PFS of 7.3 months (95% CI: 2.8, 10.8) (Chalasani 2015). Bone pain, fatigue, headache, and neutropenia were the most common AEs. Infusion-related reactions were the most common AE related to bavituximab.

A Phase II, single institution study of bavituximab and sorafenib in advanced hepatocellular carcinoma (HCC) was also conducted. Patients received 3 mg/kg IV weekly of bavituximab and 400 mg PO BID of sorafenib until radiologic progression. Secondary endpoints included overall survival, disease specific survival, 4 month progression free survival, safety, and response rate. The study accrued 38 patients. Median OS was 6.2 months. Two patients achieved partial response and four month PFS was 61%. There were no grade 4 or 5 adverse events recorded. Most common all grade events were diarrhea (32%), fatigue (26%), and anorexia (24%) (Yopp 2015). These results demonstrated that bavituximab and sorafenib were well tolerated in patients with advanced HCC.

Overall, results from Phase I and Phase II studies have demonstrated a clinically meaningful treatment effect of bavituximab, and results were consistent among the studies. The overall safety profile of bavituximab was acceptable, and the safety data were consistent with those observed in other clinical studies. Combination therapy did not substantially increase the risks of side effects. Thus the potential additional benefits of combination therapy are likely to outweigh the risk of AEs experienced during bavituximab treatment. Refer to the Investigator's Brochure for additional details.

2.3 Other Agent(s)

Temozolomide will be given as per standard of care.

2.4 Rationale

Bavituximab is a chimeric (human/mouse) monoclonal antibody (mAb) derived from murine mAb 3G4 that targets phosphatidylserine (PS) after binding to β 2-glycoprotein 1 (β 2-GP1). PS is expressed on GBM cells and targeting PS in GBM xenografts models has shown efficacy in killing tumor cells (Blanco 2014; Blanco 2015). In addition to immune activation, targeting PS has also been shown to have anti-angiogenic effects in GBM xenograft models as well as other models – an additional potential mechanism of tumor cell kill in a tumor characterized by neovascularization (Wojton 2013; Ran 2005). PS appears to be very specific for GBM cells so has also been suggested as a diagnostic imaging agent to identify tumor (Blanco 2014; Blanco 2015).

Radiation therapy increases PS expression in GBM cell lines suggesting a strong rationale for combining radiation with a drug like bavituximab that targets PS (Nida 2015). Temozolomide, the chemotherapy used in conjunction with radiation for newly diagnosed GBM, is an apoptosis inducing agent and works synergistically with radiation to induce tumor cell kill. Prior studies using SapC-DOPS, nanovesicles formed by coupling sphingolipid activating protein saposin C (SapC) and dioleoylphosphatidylserine (DOPS), interact with PS and when used in conjunction with temozolomide, there was an increase in tumor cell kill (Wojton 2014). Consequently, the triple punch combination of radiation, temozolomide, and an agent such as bavituximab appears to hold great therapeutic potential in newly diagnosed GBM.

PS is also a highly immunosuppressive membrane phospholipid and acts as an upstream immune checkpoint. In normal non-tumorigenic cells, PS is segregated to the inner leaflet of the plasma membrane but becomes externalized to the outer leaflet of the plasma membrane in cells in the tumor microenvironment (tumor cells, exosomes, and vascular endothelial cells). Phosphatidylserine is recognized and bound by PS receptors on immune cells where it induces and maintains immune suppression. In the absence of a tumor microenvironment and PS-exosome mediated signaling, this process occurs under conditions of normal cell death and immune phagocytic cell clearance (Birge 2016).

Phosphatidylserine-targeting agents block PS-mediated immunosuppression by multifocal reprograming of the immune cells in the tumor microenvironment to support immune activation (Yin 2013). Antibody-mediated PS blockade reduces the levels of myeloid-derived suppressor cells (MDSC), transforming growth factor-beta (TGF- β), and interleukin (IL) -10, and increases the levels of tumor necrosis factor-alpha (TNF- α) and IL-12. Phosphatidylserine blockade also repolarizes tumor-associated macrophages (TAMs) from predominant M2 to predominant M1 phenotype, promotes the maturation of dendritic cells (DCs), and induces potent adaptive antitumor T-cell immunity (Burrows 1994, Denekamp 1993).

Experimental studies have shown that bavituximab binds to PS in the presence of β 2-GP1 as a high affinity complex, modulating β 2-GP1 binding to PS from 1 μ M to 1 nM. In experimental cancer models, bavituximab treatment reduced tumor growth and prolonged survival, where the anti-tumor effects are enhanced by co-administration of chemotherapy or radiation (conditions that increase expression of PS).

Thus, blocking PS with bavituximab may reverse the tumor immunosuppressive environment (Yin 2013). In GBM, tumor associated macrophages (TAMs) are the predominate infiltrating immune cell and most of these are M2 cells with an anti-inflammatory phenotype (Li 2012). PS appears to play a role in maintaining this M2 phenotype in cancer and ultimately promoting T cell tolerance (Yin 2013). Blocking PS may shift the immunosuppressive phenotype driven by TAMs in GBM to a more active immunesurveillance phenotype. Furthermore, combining antiphosphatidylserine antibody with radiation induces GBM tumor immunity (He 2009). Therefore, targeting PS and reversing immunesuppression in newly diagnosed GBM with bavituximab is a novel therapeutic avenue for this devastating disease. Our clinical trial will include correlative studies that will evaluate the immune system, vascular biology and tumor microenvironment to understand the impact bavituximab is having in GBM patients.

In sum, these data support evaluation of bavituximab in GBM because:

1. PS is highly expressed on GBM tumor endothelial cells and tumor cells (Blanco 2014; Blanco 2015; Nida 2015)

2. PS is very specific for tumor as evidenced by interest in using PS as a target in diagnostic imaging as well as a target for local delivery of chemotherapy (Zhang 2014; Blanco 2014; Blanco 2015; Winter 2015).

3. Targeting PS can have anti-angiogenic properties in GBM which is attractive in a tumor characterized by vascular proliferation (Wojton 2013).

4. Targeting PS has shown tumor cell kill in GBM models (Blanco 2014; Blanco 2015; Wojton 2013; Woljton 2014).

5. There is synergism between targeting PS and temozolomide in GBM (Wojton 2014).

6. There is synergism between targeting PS and radiation in GBM xenograft models (He 2009; Nida 2015).

7. Targeting PS can relieve tumor immunosuppression and GBM is a cancer characterized by immunosuppression (Yin 2013; He 2009)

8. Bavituximab has been testing with other cytotoxic chemotherapies without increase in toxicity (see Section 2.2)

Unfortunately, there are limited options for GBM with no new drugs FDA approved since temozolomide was approved in 2005 so we desperately need better therapies. Patients in this trial will receive current standard of care treatment so do not miss out on the therapeutic benefit of standard of care but will also receive bavituximab in the hopes of augmenting the limited response to standard of care.

2.5 Correlative Studies Background

Hypothesis

GBM is considered a relatively low mutational load tumor so we hypothesis that radiation will increase antigen presentation and improve outcomes when combined with bavituximab in newly diagnosed GBM. The underlying mechanisms for this improved response can be measured using blood and MRI markers of immune status, vascular biology, and the tumor microenvironment.

Based on this hypothesis, we propose evaluating the following correlative markers:

1. Correlate baseline and change in circulating immune cell biomarkers and cells within the resected tumors (i.e. from blood as well as histological samples) with radiographic response (RR), progression free survival (PFS), and overall survival (OS).

2. Determine if changes in MRI parameters (specifically changes in perfusion, vascular permeability, or tissue cellularity/metabolism) will shed light on the mechanism of action of bavituximab in GBM.

3. Determine if changes in MRI parameters (specifically changes in perfusion, vascular permeability, or tissue cellularity/metabolism) will help distinguish responders from nonresponders early in the course of bavituximab therapy.

4. Determine if changes in MRI parameters (specifically changes in perfusion, vascular permeability, or tissue cellularity/metabolism) will help distinguish a positive inflammatory response from active tumor.

5. Determine changes in PS exosomes and serum B2GP1 during treatment with bavituximab.

Blood will be analyzed for circulating immune cells to help distinguish inflammation from active tumor by tracking T cell receptor (TCR) repertoire and its correlation with TCRs that expand in the tumor. In addition, myeloid cells will be analyzed to detect changes with therapy.

Tumor tissue will be analyzed for myeloid cells and T cells using single cell RNA-seq (fresh tissue) or population RNA-seq (fixed tissue), which will provide information about changes in myeloid cells with treatment as well as TCRs present in infiltrating T cells. If patient requires further surgery, tissue will be analyzed again for changes in myeloid cells and TCRs with therapy. This will allow for pre- and post-therapy comparison.

Preliminary data

MRI

We have conducted several clinical trials that incorporate advanced imaging to shed light on tumor response to treatment (Batchelor 2013, Gerstner 2016, Gerstner 2015). Most relevant to this proposal, we have looked at MRI changes in newly diagnosed GBM patients receiving standard radiation and temozolomide with or without cediranib, a tyrosine kinase inhibitor of VEGF receptors (Batchelor 2015). These data demonstrate our ability to analyze complex imaging datasets but, more importantly shed light on how anti-angiogenic therapy might be helping during chemoradiation. We found that increased tumor perfusion was associated with improved survival with cediranib therapy suggesting a vascular normalization effect in a subset of patients leading to improved delivery of chemotherapy and oxygen needed for radiation to be effective. In our patients treated with standard chemoradiation, we did not see this change in

perfusion. Therefore, our MRI techniques were able to shed light on the physiological impact the drug was having on GBM. Both of these datasets will be available to compare to data derived from this proposal so we will be able to determine how immunotherapy impacts tumor differently from standard therapy or anti-angiogenic therapy. Furthermore, there is a complex interaction between tumor vasculature and the immune system and our MRI, which captures vessel size and permeability as well as perfusion and blood volume, will be able to shed light on this complexity by measuring structural and functional changes in tumor vasculature longitudinally.

Vessel architectural imaging (VAI), derived from the MR perfusion acquisition, can distinguish between responders and non-responders treated with immunotherapy by measuring changes in tissue oxygenation status (SO2). Patients with metastatic melanoma to the brain treated with stereotactic radiosurgery +/- ipilumimab experienced changes in vascular structure and function. Shorter surviving patients experienced worsening in SO2 relative to healthy tissue suggesting that the immunotherapy was not effectively modulating vasculature or ultimately killing the tumor itself (Digenes 2016). Hypoxia is a negative prognostic marker in cancer so a decrease in the tissue oxygenation status (i.e. decrease in SO2) suggests that the tumor is actively growing – a fact supported by the shorter survival in these patients. The improvement in SO2 suggests vascular remodeling in response to therapy. These findings are similar to our experience in glioblastoma where a decrease in SO2 compared to healthy tissue was associated with shorter survival. We will include monitoring of tissue oxygenation, perfusion, and vascular permeability in this clinical trial to help assess tumor response.

Immunomonitoring

The [name] lab has analyzed myeloid cells in both blood and tumor tissue in depth using flow cytometry and single cell RNA sequencing (scRNA-seq). For example, they can identify 6 types of dendritic cells and 4 types of monocytes using scRNA-seq, allowing an unbiased analysis of the myeloid compartment. In addition, both myeloid and T cells can be seen by scRNA-seq of tumors pre- and post immune therapy. They have also analyzed TCR repertoire using scRNA-seq and identified enriched clones expressing a specific pair of TCR α/β in patient tumors. For FFPE samples, the [name] lab has published methods to analyze the T cell responses using bulk RNA-seq (Rooney 2015).

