9.2 Laboratory Correlative Studies

9.2.1.1 Blood for flow cytomety

Blood will be analyzed for circulating immune cells to help distinguish inflammation from active tumor by tracking T cell receptor (TCR) repertoire and its correlation with TCRs that expand in the tumor. In addition, myeloid cells will be analyzed to detect changes with therapy.

We will perform a flow cytometry analysis of myeloid cells, focusing on the number of (myeloid derived suppressor cells (MDSCs). We will use flow cytometry to analyze myeloid cells (HLA-DR+, CD3-, CD19-, CD56) cells, including CD14+ and CD16+ monocytes, DC subtypes (CLEC9A/CD141; CD1C+; CLEC9A-CD1C-), and MDSCs (CD33+CD11b+Lin-HLADR-, CD14+CD11b+Lin-HLADR- and CD15+CD11b+Lin-HLADR-) This will quantify the absolute number and frequencies of these cell types pre and post therapy. In addition, we will track TCR repertoire using standard next generation sequencing approaches (amplify TCRbeta from blood and analyze repertoire). A prior study in vaccinated glioblastoma patients demonstrated coordinate changes in TCR repertoire in tumor and blood in association with durable responses. (Hsu 2016)

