9.2.1.2 Collection of Specimen(s)

Blood will be collected prior to start of treatment, at the end of chemoradiation (week 6 of chemoradiation), first week after radiation, and then monthly for the subsequent 2 months during bavituximab + monthly temozolomide treatment.

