9.2.1.3 Handling of Specimens(s)

At appropriate time points, 50 cc of fresh whole blood will be collected in K2 EDTA 10 ml Blood Collection Tubes, delivered immediately after collection at room temperature (no ice) to [name] laboratory ([name]) for isolation and storage of peripheral blood mononuclear cells (PBMC's). Label subject ID, date and time of collection. Site will be responsible for all of the supplies, inclusive of packaging and shipping materials and shipping charges. Contact [name] ([contact]) to arrange delivery (or [contact]) Monday through Friday 8:00am - 4:00 pm.

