10. STUDY CALENDAR

Baseline evaluations are to be conducted within 2 weeks prior to start of protocol therapy. Scans must be done \leq 2 weeks prior to the start of therapy. In the event that the participant's condition is deteriorating, laboratory evaluations should be repeated within 48 hours prior to initiation of the next cycle of therapy.

Assessments must be performed prior to administration of any study agent. Study assessments and agents should be administered within \pm 3 days of the protocol-specified date, unless otherwise noted.

	Pre-	Wk	Wk	Wk	Wk	Wk	Wk	Off Treatment ^e
	Study	1^{g}	2	3	4	5	6	On meannent
Bavituximab		Х	Х	Х	Х	х	Х	
Temozolomide		Х	Х	Х	Х	х	Х	
Radiation ^J		Х	Х	Х	Х	х	х	
Informed consent	Х							
Demographics	Х							
Medical history	Х							
Concurrent meds	Х	Х		Х			Х	
Physical exam ¹	Х	Х		Х			Х	Х
Vital signs ¹	Х	Х	Х	Х	Х	х	х	Х
Height	Х							
Weight ¹	Х	Х		Х			Х	
Performance status ¹	Х	Х		Х			Х	Х
Drug diary for temozolomide ^h		Х	X	Х	Х	X	Х	

Cycle 1: Radiation + temozolomide + bavituximab

CBC w/diff, plts	Х	X	Х	Х	Х	Х	Х	х
Serum chemistry ^a	Х			х				х
PT/INR/aPTT	Х							
ECG (as indicated)i	Х							
Adverse event evaluation		X		Х			х	Х
Tumor measurements via MRI ^b	Х							Х
B-HCG °	Х							
Tissue ^{d, k}	Х							
Correlative Blood Draws f	Х						Х	

b- MRI to be done at the Martinos Center for Biomedical Imaging

c – Serum Pregnancy Test (for women of childbearing potential)

d – Assessment to determine if there is sufficient tissue for correlative studies. Tissue may be sent as a batch later to minimize shipping requirements. Tissue is not required for registration.

e- This column included in case patient goes off study during cycle 1. This visit can occur within 2 weeks of the participant coming off study.

f – See section 9.2. Blood will be drawn prior to start of chemoradiation and during week 6 of chemoradiation.

g- First bavituximab infusion should happen after the 4th radiation treatment and before the 6^{th} treatment.

h- See Appendix B for the required drug diary.

i - if ECG is clinically indicated, the QTc-B rather than QTc-F should be used to look for abnormalities

J – Radiation dose not have to be done at a DFHCC site but should be considered to allow for ease of dosing bavituximab during radiation

K – MGMT status will be collected but is not required for registration

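### Correlative item 5 in section 2.5 (change in PS exosomes and serum B2GP1) has no supporting specimen or assay in section 9.2

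*Combined protocol and SAP*

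**What the plan says.** Section 2.5 lists five correlative markers to be evaluated. The fifth is to "Determine changes in PS exosomes and serum B2GP1 during treatment with bavituximab". It names two analytes, gives a matrix (serum) for one of them, and asks for change over treatment.

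Section 9.2.1 is the plan for correlative blood.

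- **Assays (9.2.1.1).** Two are named: "We will perform a flow cytometry analysis of myeloid cells" and "we will track TCR repertoire using standard next generation sequencing approaches".
- **Timing (9.2.1.2).** "Blood will be collected prior to start of treatment, at the end of chemoradiation (week 6 of chemoradiation), first week after radiation, and then monthly". Two such monthly draws are planned, which makes five draws in all.
- **Tubes (9.2.1.3).** "50 cc of fresh whole blood will be collected in K2 EDTA 10 ml Blood Collection Tubes".
- **Processing (9.2.1.3).** The tubes go to a laboratory "for isolation and storage of peripheral blood mononuclear cells (PBMC's". No other processing step is given.

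The correlative blood rows of the section 10 calendars refer back to section 9.2. The cycle 1 footnote adds only timing: "Blood will be drawn prior to start of chemoradiation and during week 6 of chemoradiation". Section 13.4 covers blood biomarkers generically, as exploratory and as data permit, and names neither exosomes nor B2GP1.

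**The concern.** Exosomes and B2GP1 are measured in the fluid fraction of blood. The only processing step in section 9.2 keeps cells. For B2GP1 there is a second mismatch: the item asks for serum, and the specified tube is anticoagulated, so it cannot yield serum.

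The item is also tied to the drug's stated target. Section 2.2 describes bavituximab binding B2GP1 to form a complex with PS, and lists exosomes among the places where PS is exposed. A reader of section 2.5 would expect results on these two analytes.

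The timing makes the gap costly. Change during treatment needs a pre-treatment value from the same participant. If no fluid is kept at the first draw, that value is lost for good, whatever is added to the plan later.

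**Working it through.** No figure is stated for this item, so there is none to reproduce. The check is a trace of each item from section 2.5 to the section that would deliver it.

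| Item in section 2.5 | Specimen or scan | Where it is made operational |
|---|---|---|
| 1. Immune cells in blood and tumor | EDTA blood to mononuclear cells; fresh or fixed tissue | 9.2.1 and 9.2.2 |
| 2 to 4. MRI parameters | Baseline, pre-cycle 3 and post-cycle 4 research MRI | 9.1 |
| 5. PS exosomes and serum B2GP1 | None stated | None found |

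For item 5 the trace runs as follows.

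1. **Text after the list in 2.5.** The paragraph on blood covers circulating immune cells, the T-cell receptor repertoire and myeloid cells. Neither analyte appears.
2. **Assay (9.2.1.1).** Flow cytometry and receptor sequencing only.
3. **Tube (9.2.1.3).** K2 EDTA only. This rules out serum, and therefore B2GP1 in the matrix that the item names. It does not rule out plasma.
4. **Processing (9.2.1.3).** Mononuclear cells are isolated and stored. Nothing is said about the remaining fraction.
5. **Shipping and laboratories (9.2.1.4 and 9.2.1.5).** No exosome or B2GP1 work is assigned.
6. **Tissue (9.2.2).** Not relevant to a circulating analyte.
7. **Calendar (section 10).** It points back to 9.2 and adds no specimen.
8. **Analysis (13.4).** It names no analyte. Its general wording, including change during treatment, could accommodate both if data existed.

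Timing is not the obstacle. The five draws are one before treatment, one in week 6 of chemoradiation, one in the first week after radiation, and two monthly. That gives a baseline and four later values.

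Volume is not the obstacle either:

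- Tubes per draw: 50 / 10 = 5.
- If one becomes a serum tube: 4 × 10 = 40 cc remain for mononuclear cells, a loss of 10 / 50 = 20%.
- If plasma is taken from the existing tubes: no change in the volume drawn.

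**The case against.** The case for leaving this alone has several parts, and some of them stand.

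- **Other blood is drawn.** This is true. Serum chemistry and a serum pregnancy test are in the section 10 calendars, so a reader should not infer that EDTA blood is the only blood collected. But no passage provides for keeping that serum for research, and the cycle 1 calendar has serum chemistry at pre-study and week 3, not at the week 6 correlative draw.
- **The plan does not say plasma is thrown away.** This is also true. Section 9.2.1.3 sends fresh whole blood to a laboratory and is silent on what happens to the fluid. Discarding is a tempting inference, but it rests on silence. What the documents support is that no separation or storage is described.
- **The EDTA argument reaches only half of the item.** Correct. Serum qualifies B2GP1, not exosomes. For exosomes the gap is a missing processing step and assay, not a wrong tube.
- **The item could still be answered.** Yes, if plasma is set aside from the same tubes. To say that the item cannot be answered at all would go too far. It cannot be answered by following section 9.2.1.3 as written.
- **It is not a trial objective.** Sections 1.2 and 1.3 list OS12, progression-free survival and toxicity. Item 5 sits in a background section, and its analysis is exploratory.

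What remains is the core: a stated correlative aim with no specimen, processing step, assay or laboratory behind it.

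**Conclusion.** The gap is real and limited. One of the five correlative items in section 2.5 has no supporting specimen or assay, at any of the five draw times in section 9.2.1.2. For B2GP1 the specified tube also contradicts the named matrix. The conclusion rests on two things: that EDTA blood yields plasma but not serum, and that no separate laboratory instruction exists. None is referenced in the protocol.

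Three stronger readings should be resisted.

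- **A count of lost samples.** Multiplying five draws by 36 participants gives 180, but that assumes that everyone attends every draw and that all plasma is discarded. The documents establish neither.
- **A claim that bavituximab acts only through B2GP1, or that these analytes are its most direct readout.** Section 2.2 gives the primary mechanism as modulation of the tumor microenvironment, through Fc-mediated signaling and direct cell killing. The protocol does not rank these analytes above the cell and MRI markers.
- **A threat to the main result.** OS12, the sample size and the error rates do not depend on this item.

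It is still worth correcting. The missing baseline cannot be made good later, and the correction costs little.

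**What to change.** Choose one of the following before baseline draws are taken.

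1. **Plasma from the existing tubes.** In section 9.2.1.3, have the receiving laboratory separate, aliquot and freeze plasma before mononuclear cell isolation at every correlative draw. Restate item 5 as plasma PS exosomes and plasma B2GP1. Cost: a short paragraph, cryovials and freezer space. There is no extra visit, draw or blood.
2. **A serum tube, if serum is required for B2GP1.** Replace one of the about five EDTA tubes with a serum tube within the same 50 cc, and still save plasma from the others for exosomes. Cost: about one fifth less blood for mononuclear cells. The laboratory should confirm that 40 cc is enough for the flow cytometry and receptor sequencing.
3. **Delete item 5**, if the assays are not intended.

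Under 1 or 2, name the assay and the responsible laboratory for each analyte in section 9.2. In section 13.4, add the within-participant change from baseline in both analytes to the exploratory blood biomarkers, using the same matrix at every draw.
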